3.3.8 Immunogenicity

Samples for Anti-drug antibodies (ADA) will be collected before administration of study medication according to the SoA (CSP Table 3). ADA variables, such as ADA responses, will be generated and analyzed as per the details in Appendix 8.2.

ADA information that would unblind the study will not be reported to investigative sites or blinded personnel until the study has been unblinded.

All available data will be included, regardless of intercurrent events like taking rescue medication or withdrawal from study.

3.3.9 Investigator Global Assessment (IGA) at Week 52

The IGA is defined for the primary endpoint variable above (Section 3.2).

The proportion of participants with an IGA 0/1 and a decrease in IGA of ≥ 2 points at Week 52 relative to baseline will be analyzed.

Intercurrent events will be considered as described above in Section Intercurrent Events (Section 3.1.5). Participants with a missing baseline IGA score will have missing responder status at post baseline visits. Intercurrent events will be considered for analyses and descriptive summaries.

3.4 Safety outcome variables

Safety and tolerability will be evaluated in terms of: reported AEs (including serious adverse events (SAEs)), vital signs, physical examination, electrocardiogram and clinical laboratory assessments.

All safety measurements will use all available data for analyses, including data from unscheduled visits and repeated measurements.

Change from baseline to each post-treatment time point where scheduled assessments were made will be calculated for relevant measurements. Safety data will be summarized by means of descriptive statistics and qualitative summaries.

The handling of partial/missing dates for classifying AEs is detailed in Appendix 8.3. Duration of AEs will not be calculated using imputed dates and will instead be set to missing. No other safety data will be imputed.

3.4.1 Adverse Events

AEs (including SAEs) experienced by the participants will be collected throughout the entire study and will be coded using the latest version of the Medical Dictionary for Regulatory Activities (MedDRA) that will have been released for execution at AstraZeneca/designee per the Data Management Plan.

AEs for the 16-week placebo-controlled analysis reporting will include all AEs with start date prior to entering the extension period.

AEs for the Week 52 end of study reporting over the entire study duration will include all AEs as defined below. AEs reported for the extension period alone are those with start date on or after the date of first dose of treatment during the extension period.

As per CSP Section 9.4.3, the following events are considered treatment emergent:

- AEs with an onset date on or after the first dose of IP;
- Worsening of pre-existing events on or after first dose of IP.

For the analysis, an AE will be defined as Treatment Emergent AE (TEAE) if it has an onset date on or after the first dose of IP. Applying this definition, also the worsening of pre-existing events on or after the first dose of IP will be included in the analysis as Investigators are instructed to record these as new events.

AE data will be categorized according to their onset date into the following study periods:

- AEs in the pre-treatment period are defined as those with an onset prior to the day of first dose of IP.
- AEs in the on-treatment period for 16-week placebo-controlled period are defined as those with onset date between day of first dose of IP and the day prior to first dose in extension period; or the last dose in placebo-controlled period + 30 days for those who do not enter the extension period.
- AEs in the on-treatment period for extension period only are defined as those with onset date between day of first dose of IP in the extension and the last dose + 30 days.
- AEs in the on-study period for Week 52 end of study reporting are defined as those with onset on or after the day of first dose of IP.

If an AE has a missing onset date then unless the stop date of the AE indicates otherwise, this will be considered an on-treatment AE. Similarly, if an AE has a partial onset date, then unless

the partial onset date or the stop date indicates otherwise, this will be considered an on-treatment AE.

AEs that have missing causality (after data querying) will be assumed to be related to study drug.

3.4.2 Clinical laboratory variables

Blood and urine samples for determination of clinical chemistry, hematology and urinalysis parameters will be taken at the times detailed in the CSP and will be assessed in a central laboratory. The parameters outlined in Section 8.2.1, Table 10 of the CSP will be collected.

In summaries, figures, and listings, lab results and normal ranges will be presented in System International (SI) units. Eosinophil data will be presented in both SI and conventional units (cells/ μ L) in summaries.

Changes in hematology and clinical chemistry variables between baseline and each post-baseline assessment will be calculated. For values recorded with a leading greater than or less than ('>', '<') symbol, the reported numeric value will be used for analysis and the value with the symbol will be included in the listings, unless otherwise specified. For example, a value of <0.01 will be analyzed as 0.01 and listed as <0.01.

Absolute values will be compared to the relevant reference range and classified as low (below range), normal (within range or on limits) or high (above range). The central reference ranges will be used for laboratory variables. All absolute values falling outside the reference ranges will be flagged.

Maximum or minimum value post-baseline will be calculated over the on-treatment period. This will be defined at both reporting occurrences, the 16-week placebo-controlled analysis reporting and the Week 52 end of study reporting.

For the liver function tests: aspartate aminotransferase (AST), alanine aminotransferase (ALT), alkaline phosphatase (ALP), gamma-glutamyl transpeptidase (GGT) and total bilirubin (TBL), the multiple of the central laboratory upper limit of the normal (ULN) range will be calculated for each data point.

$$\text{Multiple} = \text{Value} / \text{ULN}$$

That is, if the ALT value was 72 IU/L (ULN=36) then the multiple would be 2.

Urinalysis data with qualitative results will be categorized as negative (0), positive (+), or strongly positive (++, +++, or >++) at each timepoint.

3.4.3 Vital signs, physical examination and electrocardiogram

Pre-dose vital signs (pulse, systolic blood pressure, diastolic blood pressure, respiration rate, body temperature, body weight, and height) will be obtained in accordance with the schedule provided in Table 3 of the CSP. Body temperature will be measured in Celsius in accordance with local standards; weight will be recorded in kilograms.

Body mass index (BMI) will be calculated from the height and weight as follows:

$$BMI (kg/m^2) = Weight (kg) / (Height (m))^2$$

Changes in vital signs variables between baseline and each subsequent scheduled assessment will be calculated.

Absolute values will be compared to the reference ranges in Table 8 and classified as low (below range), normal (within range or on limits) or high (above range). All values (absolute) falling outside the reference ranges will be flagged.

Table 8 Vital signs reference ranges

Parameter	Standard Unit	Lower Limit	Upper Limit
Diastolic Blood Pressure	mmHg	60	120
Systolic Blood Pressure	mmHg	100	160
Pulse Rate	Beats/min	40	120
Respiratory Rate	Breaths/Min	8	28
Body Temperature	Celsius	36.5	38
Weight	kg	35	200

Physical examinations (complete or brief), including height and weight, will be conducted in accordance with the schedule provided in Table 3 of the CSP. Any new findings or aggravated existing abnormalities, judged as clinically significant by the Investigator, will be reported as an AE as described in CSP Section 8.3.5.

The complete physical examination will include an assessment of the following: general appearance, skin, head and neck (including eyes, ears, nose, mouth, and throat), lymph nodes, abdomen, musculoskeletal (including spine and extremities), cardiovascular, respiratory, and neurological systems. The brief physical examination will include an assessment of the general appearance, abdomen, cardiovascular, and respiratory system. For both types of physical examination, only information on whether the assessment was performed or not is to be recorded.

Single 12-lead electrocardiogram (ECG) will be obtained locally during screening (Table 3 of CSP) using an ECG machine that automatically calculates the heart rate and measures PR,

QRS, and QT intervals. The ECG results will be interpreted locally for the overall interpretation (normal/abnormal) and determination of clinical significance of any potential ECG findings (yes/no) and abnormal reason, which will be recorded in the eCRF.

3.5 Tertiary/exploratory outcome variables

3.5.1 Healthcare resource utilisation

At randomization, retrospective AD-related healthcare resource utilization information will be collected with a one-year recall period. At all subsequent visits (see CSP Table 3), AD-related healthcare resource utilization information will be collected with a recall period of ‘since last scheduled visit’.

The data collected may be used to conduct exploratory economic analyses and include:

- Number and duration of hospitalization (length of stay, overall and by wards [eg, general ward, intensive care unit]);
- Number and type of diagnostic and therapeutic tests and procedures;
- Number of outpatient medical encounters and interventions (including GP, specialists, or emergency room visits, and medications).

Note: Cases of hospitalization occurring after signing of the ICF must be reported as an SAE (CSP Section 8.3).

All available data will be included, regardless of taking rescue medication or withdrawal from study.

Healthcare resource utilisation will be summarized descriptively. Any additional analyses will be performed separately and not form part of this SAP.

3.5.2 Hospital Anxiety and Depression Scale (HADS)

The Hospital Anxiety and Depression Scale (HADS) will be completed at the on-site visits specified in the SoA (CSP Table 3) on the electronic device supplied to the site.

The HADS is a mental health assessment comprising 7 items on anxiety and 7 items on depression. All questions are rated on a 0 to 3 scale, with higher scores representing worse mental health; scores each of for the 2 subscales thus range from 0 to 21. Scores between 0 and 7 are considered normal, scores between 8 and 10 are possible cases of anxiety/depression, scores 11 or greater are considered likely cases of anxiety/depression. The ePRO does not allow for questions to be unanswered, so no consideration is required for missing items.

Intercurrent events will be considered as described above in Section Intercurrent Events (Section 3.1.5). Intercurrent events will be considered for analyses and descriptive summaries.

The change from baseline in HADS anxiety and depression scores will be analyzed at Week 16 and at Week 52.

3.5.3 Patient Global Impression of Severity (PGI-S)

The Patient Global Impression of Severity (PGI-S) will be completed at the on-site visits specified in the SoA (CSP Table 3) on the electronic device supplied to the site.

The PGI-S is a single item assessment of the participant's perception of overall symptom severity "over the past 7 days". The assessment uses a 6-point categorical response scale (0 = no symptoms, 1 = very mild, 2 = mild, 3 = moderate, 4 = severe, 5 = very severe). The ePRO does not allow for questions to be unanswered, so no consideration is required for missing items.

All available data will be included, regardless of intercurrent events like taking rescue medication or withdrawal from study.

The PGI-S will be summarized descriptively.

3.5.4 SF-36 (Version 2), Acute Recall

The Short Form 36-item Health Survey Version 2 (acute recall) (SF-36v2) will be assessed at on-site Visits 1, 2, 6, 7, 12, 16, and IPD visit, and at home every 28±3 days after Visit 2 until Visit 6 is confirmed, on the electronic device supplied to the participants.

SF-36v2 is a 36-item questionnaire on functional health and well-being. The recall period is 1 week. Responses to 35 of the 36 items are used to compute 8 domain scores and 2 component summary measures. The remaining item (the "Health Transition" item) asks participants to rate how their current state of health compares to their state of health 1 week ago. The Health Transition item is not used to calculate the domain scores.

The 8 domains are: Physical Functioning (PF), Role Limitations due to Physical Health (RP), Bodily Pain (BP), General Health Perceptions (GH), Vitality (VT), Social Functioning (SF), Role Limitations due to Emotional Problems (RE), and Mental Health (MH). The component summary measures (physical component summary [PCS] and mental health component summary [MCS]) are computed from domain scores to give a broader metric of physical and mental health-related quality of life. The transformed score range for each of the 8 domains and for PCS and MCS is 0-100; higher scores indicate better health state. The ePRO device does not allow for questions to be unanswered, so no consideration is required for missing items.

The change from baseline in SF-36v2 (PCS and MCS) scores will be calculated.

The threshold values for the SF-36v2 PCS, MCS, and domain scores listed in [Table 9](#) are suitable for interpreting change at the participant level and are referred to as the responder thresholds or responder definitions ([Maruish 2011](#)).

Table 9 Threshold Values for the SF-36v2 Scale and Summary Measures

Threshold	SF-36v2 score									
	PCS	MCS	PF	RP	BP	GH	VT	SF	RE	MH
Group difference	2	3	3	3	3	2	2	3	4	3
Individual change	3.4	4.6	4.3	3.4	6.2	7.2	6.2	6.9	4.5	6.2

[figure not shown]
BP, Bodily Pain; GH, General Health Perceptions; MCS, mental health component summary; MH, Mental Health; PCS, physical component summary; PF, Physical Functioning; RE, Emotional Problems; RP, Role Limitations due to Physical Health; Short Form 36-item Health Survey Version 2; VT, Vitality.

Categorical analyses of the change in each of the SF-36v2 scales and summary measures will be compared to its respective individual change threshold (see [Table 9](#)) to indicate whether each participant experienced a change deemed clinically significant and important. A participant will be classified as a responder if the change from baseline \geq individual change threshold, or a non-responder if change from baseline $<$ individual change threshold. If data are missing, then the participant will be classified as a non-responder.

Intercurrent events will be considered as described above in Section Intercurrent Events (Section [3.1.5](#)). Intercurrent events will be considered for analyses and descriptive summaries.

The change from baseline in SF-36v2 PCS and MCS will be analyzed at Week 16, and at Week 52.

CCI

CCI

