[Figure 1](#) presents an overview of investigational product (IP) administration for each randomized treatment group.

Figure 1 Investigational Product Administration Q4W by Randomized Treatment Sequence

^a In the extension phase, participants will receive benralizumab on a Q8W or Q4W dosing regimen, as predetermined at randomization (Visit 2). Participants randomized to receive benralizumab Q8W in the extension phase will also receive placebo at intervening study visits when they are not receiving benralizumab.

Q4W, every 4 weeks; Q8W, every 8 weeks.

All participants who prematurely discontinue IP (IPD) should return to the study site for the IPD visit 4 weeks (± 7 days) after the last dose of IP for procedures, or as soon as feasible if this interval is missed (eg, if decision on discontinuation was made later), as specified in Table 3 of the CSP.

[figure not shown]
At the IPD visit, the participant will be offered the following options for further follow-up:

- Participants are encouraged to return to all scheduled site visits and perform all procedures but without IP administration, until the end of the study (Visit 16).
- Participants unwilling or unable to attend the scheduled site visits until the end of the double-blind treatment period, will be offered a follow-up option that includes monthly telephone contact instead. During follow-up telephone contact, the Investigator will collect information about concomitant medications, information on AD symptoms, and AE/SAE(s).

All Week 16 analyses at primary database lock (DBL) will evaluate the two initial dose treatment arms: benralizumab 30 mg (total $n = 80$), and placebo (total $n = 80$). Analyses of data for Week 52 end of study reporting will include data from the entire study, presenting the three randomized treatment groups: benralizumab followed by Q4W, benralizumab followed by Q8W and placebo followed by benralizumab Q4W-Q8W.

For an overview of the study design, see [Figure 2](#). For further details see CSP Section 4.1.

Figure 2 Study Design

^a To maintain blinding, participants will receive investigational product every Q4W during the extension period. Placebo will be administered Q8W, occurring 4 weeks after each benralizumab administration. n, number; Q4W, every 4 weeks; Q8W, every 8 weeks.

Participants and Investigators will remain blinded to the treatment and regimen until the final DBL.

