1.1.2 Investigational Product Dosing Regimen

Participants who meet entry criteria will be randomized 1:1:2 by the interactive voice/web response system (IxRS) to 1 of the 3 treatment sequences described in Section 1.1.

Blinded IP (benralizumab or placebo) will be administered Q4W at Weeks 0, 4, 8, and 12 (Figure 1).

From Week 16 onwards, participants initially randomized to benralizumab 30 mg will receive benralizumab 30 mg Q4W or Q8W interval, according to their original randomization at Visit 2 (Week 0) (Figure 1).

At Weeks 16, 20, and 24, participants initially randomized to placebo will receive benralizumab 30 mg Q4W. At Week 28, these participants will transition to receive benralizumab 30 mg Q8W interval (Figure 1).

All participants on Q8W regimen from Week 16 onwards will continue to receive treatment containing placebo at their Q4W visit intervals (Figure 1), thus maintaining the blinded treatment regimen.

The final dose of benralizumab or placebo will be administered at Week 48.

Please refer to the clinical study protocol (CSP) for more details.

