3.1.3 Visit windows

For the Peak Pruritus NRS, weekly summary scores will be calculated using the 7 daily scores for each week, starting with randomization day (e.g. Days 1 to 7 for Week 1, Days 8 to 14 for Week 2), regardless of visit attendance days.

For Peak Pruritus NRS Week 16 score, the 7 days prior to the scheduled Week 16 timepoint (ie Days 106 to 112) will be used for calculation. However, only days prior to the first dose of IP in the extension period will be used for the Week 16 score derivation. If the Week 16 visit, and therefore the start of extension period IP dosing, occurs ahead of schedule (ie at Day 112 or earlier), then the 7 days prior to this day of first dose of extension period IP will be used for the Week 16 score, and the Week 15 score will be set to missing. If the Week 16 score cannot be calculated on the 7 daily scores, then an additional 1-day shift to assess the 8 daily scores before extension IP dose day will be assessed, and the Week 15 score will be set to missing. For Week 17 score, the scheduled 7 days before day 120 (ie Days 113-119) will be used. If the Week 16 visit occurs at Day 113 or later, Days 106 to 112 will be used in the Week 16 score as planned. Further details on scoring for daily Peak Pruritus NRS will be provided in Section 3.3.2.

For efficacy endpoints that present visit-based data, visit windows will be applied. The adjusted analysis-defined windows will be based on the collection schedule listed in the protocol and variables will be windowed to the closest scheduled visit for that variable.

Visit windows following baseline will be constructed in such a way that the upper limit of the interval falls halfway between two visits (the lower limit of the first post-baseline visit will be study day 2). If an even number of days exists between two consecutive visits, then the upper limit will be taken as the midpoint value minus 1 day. Visit windows are constructed so that every observation collected can be allocated to a particular visit. No visit windows will be defined for screening visits.

For assignment of data to adjusted analysis-defined visit windows, study day will be defined as follows:

$$(Date\ of\ assessment - date\ of\ randomization) + 1$$

Following this definition, for example if the day of randomization is study day 1 and date of assessment is the planned date of Visit 3 (Week 4), the study day will be 29 (28+1).

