4.2.9.4 SF-36 (Version 2), Acute Recall

The number and percentage of participants above and below the threshold values for the SF-36v2 Scale domains, PCS and MCS will be presented. The binary endpoints will be analyzed at Week 16 and at Week 52 using logistic regression models in a similar way to that described for the primary endpoint analyses (Section 4.2.6.1).

Descriptive summary statistics for scores and change from baseline will be produced by treatment group and visit.

CCI

CCI

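### The SF-36v2 visit list in SAP 3.5.4 appears to omit the Week 52 visit at which 3.5.4 and 4.2.9.4 analyse it, so list and analysis must be reconciled

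*SAP*

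**What the plan says.** - **Collection.** SAP 3.5.4 says the SF-36v2 "will be assessed at on-site Visits 1, 2, 6, 7, 12, 16, and IPD visit". It is also completed "at home every 28±3 days after Visit 2 until Visit 6 is confirmed", so no home records are planned in the extension.
- **Change from baseline.** SAP 3.5.4: "The change from baseline in SF-36v2 PCS and MCS will be analyzed at Week 16, and at Week 52".
- **Responders.** SAP 4.2.9.4: "The binary endpoints will be analyzed at Week 16 and at Week 52 using logistic regression models". These cover the eight domains and the two summary scores.
- **Missing responder data.** SAP 3.5.4: "If data are missing, then the participant will be classified as a non-responder".
- **Visit anchors.** SAP 1.1.2 places Visit 2 at Week 0 ("according to their original randomization at Visit 2 (Week 0"). SAP 3.1.3 places Visit 3 at Week 4 ("date of assessment is the planned date of Visit 3 (Week 4"). SAP 1.1.2 has visits every 4 weeks, with the last dose at Week 48. SAP 2.1 and 4 add the end of the 52-week treatment period and a Week 60 follow-up. SAP 1.1.1 names Visit 16 as the last visit ("until the end of the study (Visit 16").

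**The concern.** The SAP fixes a Week 52 analysis of the SF-36v2, but the collection visits it lists for that questionnaire do not seem to include Week 52. If the list is right, the Week 52 analyses have almost no data to work on. If the analyses are right, the list is wrong, and anyone deriving expected assessments or missingness from 3.5.4 will work from the wrong schedule.

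What is at stake is the long-term SF-36v2 result. It would be either not estimable or drawn from a visit whose timing differs from its label. Nothing in the SAP tells a programmer which visit to use for Week 52.

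**Working it through.** **1. Reproduce the SAP's own figure.** With randomization on study day 1, a visit planned for week w falls on day 7w + 1. For Week 4 this gives 7 × 4 + 1 = 29, which is the worked example in SAP 3.1.3.

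**2. Count the visits.** Dosing visits at Weeks 0, 4, …, 48 number 48/4 + 1 = 13. Adding Weeks 52 and 60 makes 15. Starting at Visit 2, 15 visits run to Visit 16, the visit that SAP 1.1.1 calls the end of the study. The count closes with none left over.

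| Visit | Week | Study day | Listed for SF-36v2 |
|---|---|---|---|
| 2 | 0 | 1 | yes |
| 6 | 16 | 113 | yes |
| 7 | 20 | 141 | yes |
| 12 | 40 | 281 | yes |
| 15 | 52 | 365 | **no** |
| 16 | 60 | 421 | yes |

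**3. Distance from Week 52.** Visit 12 is 52 − 40 = 12 weeks early. Visit 16 is 60 − 52 = 8 weeks late, and 60 − 48 = 12 weeks after the last scheduled dose.

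**4. Windows.** SAP 3.1.3 assigns each value to the nearest scheduled visit for that variable. On the 3.5.4 list, consecutive visits are on Days 281 and 421, with midpoint (281 + 421)/2 = 351. The Week 40 window therefore ends on Day 350 or 351, depending on how the even-number rule is read. A value on Day 365 would go to Week 60 either way.

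**5. The IPD visit.** SAP 1.1.1 sets it 4 weeks (± 7 days) after the last dose, for premature discontinuers. If the last dose was at Week 44 (Day 309), the IPD visit is due on Day 337, range 330 to 344, which falls in the Week 40 window. A late IPD visit could come nearer to Week 52. The visit as described in 1.1.1 does not apply to participants who complete treatment.

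**6. Effect on the responder models.** If no completer has a Week 52 value and missing means non-response, the number of responders is 0, or close to it, in every group. With 0 responders the odds are 0 in each group and the log odds ratio has no finite estimate. SAP 4.2.6.1, whose approach 4.2.9.4 follows, falls back on a Cochran–Mantel–Haenszel test. In each stratum that test's variance is proportional to the number of responders, so it is also 0 and the statistic is 0/0. This would apply to all 8 + 2 = 10 responder endpoints. The change from baseline would likewise have no scheduled Week 52 value from completers.

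**7. Other visit numberings.**
- With a Week 56 visit added, Visit 16 would be Week 56 and Visit 15 still Week 52, so Week 52 would remain unlisted.
- With one unlisted visit between Weeks 4 and 16, Visits 7, 12 and 16 would be Weeks 16, 36 and 52, and the conflict would vanish. Week 60 would then be Visit 17, against SAP 1.1.1.

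**The case against.** **The weeks are inferred.** The SAP prints a week only for Visits 2 and 3. The table that settles the rest is in the protocol, which was not available for this check. This stands, and it limits how firmly the point can be put. However, 3.5.4 writes out its own visit list, whereas HADS and PGI-S (3.5.2, 3.5.3) simply refer to the protocol schedule. The inconsistency is therefore within the SAP.

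**Windows follow the protocol, not 3.5.4.** SAP 3.1.3 ties windows to the protocol's collection schedule. If that schedule has the SF-36v2 at Week 52, the window exists and the fault is one wrong visit number. This stands, and the fix allows for it.

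**The list includes IPD.** Elsewhere the SAP writes IPD and EOT together (2.1, 4, 5). If they share one schedule entry and EOT is the Week 52 visit, completers might be assessed then. The SAP does not say so, and 1.1.1 describes IPD as a visit after premature discontinuation. Some records near Week 52 remain possible, so a reader who infers that no Week 52 measurement can exist goes further than the text allows.

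**All participants as non-responders is hypothetical.** The Missing category in SAP Table 3 concerns a missed questionnaire or visit while the participant remains in the study, and an empty table would be noticed at programming. That is fair. The missing-data sentence in 3.5.4 carries no such limit, though, and noticing the problem late does not say what to analyse instead.

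**The endpoint is minor.** SF-36v2 is exploratory and outside the testing hierarchy of 4.1.1. DLQI and CDLQI, the secondary quality-of-life measures, have their own Week 52 analyses (4.2.7.7, 4.2.7.8). This stands in full.

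**Conclusion.** The point holds as an internal inconsistency. On the visit count that the SAP supports, the SF-36v2 list covers Weeks 20, 40 and 60 in the extension and omits Week 52, while two sections analyse Week 52. Followed as written, the Week 52 responder models would have essentially no scheduled completer data and could not be estimated.

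This rests on three assumptions: visits every 4 weeks with no unlisted extra visit, Visit 16 being the Week 60 follow-up, and IPD being distinct from the Week 52 visit for completers.

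Two stronger readings are not supported. One is that the long-term quality-of-life comparison of the Q4W and Q8W regimens as a whole is undermined; DLQI and CDLQI carry that at secondary level. The other is that Visit 16 values will be presented as Week 52; nothing in the SAP says so, although nothing prevents it. Primary, key secondary and safety conclusions are unaffected.

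**What to change.** Before final database lock, compare the visit list in SAP 3.5.4 with the protocol's schedule table.

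- **If the SF-36v2 is collected at the Week 52 visit:** correct the list in 3.5.4 and the identical list for EQ-5D-5L in 3.5.8, and keep the Week 52 analyses.
- **If it is not:** remove the Week 52 SF-36v2 analyses from 3.5.4 and 4.2.9.4. Analyse the last on-treatment visit actually collected (Visit 12, Week 40 on the count above). Report Visit 16 descriptively as Week 60 post-treatment follow-up, not as Week 52.

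In either case, print the week beside each visit number in 3.5.4.

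The cost is SAP wording and table shells. In the second case the long-term SF-36v2 time point becomes 12 weeks earlier than planned.
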